## Figure 2. NEONATAL SKIN CONDITION SCORE (NSCS)

#### **Dryness**

- 1 = Normal, no sign of dry skin
- 2 = Dry skin, visible scaling
- 3 = Very dry skin, cracking/fissures

[figure not shown]
#### **Erythema**

- 1 = No evidence of erythema
- 2 = Visible erythema, <50% body surface
- 3 = Visible erythema, ≥50% body surface

### Breakdown

- 1 = None evident
- 2 = Small, localized areas
- 3 = Extensive

*Note:* perfect score = 3, worst score = 9.

viii. Parent and Provider Interviews: Parents will be asked to participate in an interview about the acceptability of the intervention after their infant completes the study. Ten parents (5 in each study group) will be interviewed. The interview is not expected to last more than 30 minutes, but will largely be under the direction of the parent (see Appendix A for the interview guide). Ten providers to include at least two neonatologists, two neonatal nurse practitioners and six bedside nurses, will be asked to participate in an individual interview at the time of study completion about the acceptability and feasibility of the intervention (see Appendix B for the interview guide).

## 5. Selection of Infant Subjects

## Infant Inclusion criteria are:

- a. Must be participating in the ICN standard 3-hour bundled care
- **b.** Must wear a breathable diaper
- **c.** Must be  $\leq$  32 weeks gestation
- d. Infants are expected to remain in ICN at least 2 weeks

#### Infant Exclusion criteria are:

- 1. Neonatal Abstinence Syndrome
- 2. Humidified incubator
- 3. Diaper rash
- **4.** Pre-existing or genetic skin conditions
- **5.** Severe illness requiring 1:1 nursing care: e.g. minimal stimulation protocol, high frequency ventilation, vasopressor drug support, or body cooling.

## 6. Subject Recruitment and Compensation

Study personnel will check the daily admission log for eligible patients. Clinical staff known to the parent/guardian of the potential subject will introduce the research study to the infant's family. If the parent/guardian expresses interest in the study, the research staff will approach him/her to explain the study and request consent. There will be no compensation for study participation, however infants will be given a developmental toy at the end of the study.

### 7. Consent Process

## **Subject's Capacity to Give Legally Effective Consent**

For infants, consent will be obtained from the parent or guardian following approval of the infant's provider using see Section 14 of the e-IRB submission form and complete the questions in that section. The PI, research coordinator or other study personnel (who is either an RN or has a PhD (or both) and is trained in study and consent procedures) will conduct the consent process in the study as outlined by GCP guidelines.

Parents will be approached for pre-consent if their infant is ≤ 32 weeks gestation. The infants' medical provider, or a member of the Neonatal Perinatal Research Unit will seek permission from the mother or father for the research staff to discuss the study with them. Then, research staff (i.e. PI, study coordinator or research assistant) will contact the parent in person while visiting the ICN. If contact cannot be made with parents during visiting hours, parents will be contacted via phone. Parents will be approached at the bedside of their infant. Parents will be offered the option to discuss the study at their infant's bedside or in an available conference or meeting room on the unit. If others are present, the parent is asked whether she would prefer for the research member to discuss the study in front of her visitors or at another location (e.g. unit conference room behind a closed door).

We estimate that the consent process will take about 30-60 minutes. Parents will be allowed as much time as needed to decide whether or not to enroll the infant in the study. Parents will be encouraged to ask questions at any time before their infant's participation in the trial. The study team will present the consent form in its entirety, with special emphasis on the voluntary nature of research, and the ability of subjects to withdraw from the study at any time. No one who is obtaining consent is directly involved in the supervision of the providers who are being asked to participate in the study or involved in the direct care of the infants whose parents are being asked to participate in the study. The research staff will closely follow the IRB and GCF guidelines..

Spanish speaking parents/guardians of eligible infants will be consented using two translators that are not involved in the study, one to present the consent form in Spanish and one to assure that what is presented is correct. The translator will translate the entire English consent form verbally to the potential study subject. The translator will relay questions to the study coordinator from the subject and the subject will have questions answered prior to signing the consent document. For Spanish speaking parents/guardians, the parent/guardian and witness will be asked to sign the Spanish short form. The witness and the person obtaining consent must sign the English consent form.

Providers will be consented using the same IRB and GCF guidelines described above. Provider consent should take 15-30 minutes.

#### 8. Risk/Benefit Assessment

Risks associated with the intervention and data collection will be minimal. All of the study interventions including a less frequent diaper change are considered acceptable standard of care. The skin condition will be monitored twice daily to identify any potential change in the skin of the diapered area and if the NSCS is  $\geq 5$  due to dryness, erythema or skin breakdown in the diapered are, the intervention will be discontinued, the infant's provider will be consulted regarding the need for treatment and the infant will be monitored until resolution of the problem. The infant stress associated with stimulation due to data collection should be minimal. Data collection processes for the biomarkers should not cause discomfort and handling will be kept to a minimum. However, all research staff will have neonatal experience and be trained in developmentally appropriated infant handling and positioning.

The small risk of loss of confidentiality will be reduced by assigning code numbers to the samples. The key linking the identity of the subject to the code number will be separately maintained in the Research Office, under lock and key.

There may be a direct benefit to the subjects participating in the study including less physiological stress during caregiving or improved skin health. However, actual benefits will not be clear until future larger studies are conducted. By improving our understanding of the relationship between bundled diaper care and infant health outcomes more targeted interventions may be developed for general health, development and skin care.

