The inclusion and exclusion of certain care activities in any individual care event is often dictated by the infant's treatment plan or needs, but some activities like diapering may be optional. Understanding the impact of when to include optional, yet stress provoking interventions, will allow us to minimize overall environmental stress in hospitalized VLBW infants. It is unclear how the different times used in bundled care affect overall infant health including skin health in the diapered area. Therefore, given the lack of data around bundled care, we aim to explore the impact of bundling diaper care activities on overall health of VLBW preterm infants. We will include a focus on skin health because it is important to understand the benefits of decreased infant stress and any potential skin health trade-offs associated with longer versus shorter time between diapering care. Findings from this study will allow us to better understand the relationship between neonatal skin health while providing developmentally appropriate bundled care.

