d. Procedures: A neonatal provider will give approval for participation in the study. Parents will be approached for consent after eligibility screening is completed (≤ 32 weeks gestation). The principal investigator is a clinical nurse specialist and nurse scientist who has been affiliated in the Intensive Care Nursery since 1993. Study personnel will explain the study, allow time for questions, have a parent sign the consent form, and a copy will be given to the parent. Parents will provide consent for their infant's participation in the study and will give permission for themselves to participate in an interview about the study, if selected. Five parents from each group will purposively selected to participate in an interview. Parents will be selected to include parents with infants < 1000 grams at birth and parents with infant ≥ 1000 grams at birth.

[figure not shown]
Following consent, the infant will be monitored until all inclusion and exclusion criteria are met. At that time randomized to an intervention group and data collection will be initiated. The intervention will continue for six weeks at which time collection of data will stop and bundled diapered care will resume according to unit protocol. If the infant no longer meets inclusion criteria the intervention will be discontinued and routine data collection will be discontinued. The exclusion criteria will be noted, e.g. use of diaper cream, and data collection regarding any new illness characteristics or treatments will continue. If an infant requires a diaper change due to a stool or other needed procedure this will be recorded on a bedside card.

Ten nurses will be recruited for participation in interviews around intervention acceptability at the end of the study.

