- vii. Neonatal Skin Condition Score (see Figure 2): The NSCS will be collected twice daily (day and night shift by staff nurses) while infants are participating in the study. The NSCS is a reliable and valid measure of skin condition (Lund & Osborne, 2004)

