# **RQ2**. Do neonatal skin condition scores differ over time and at the end of 6 weeks between 3-and 6-hour bundled care diapering?

**Analysis:** We will assess the distribution of the neonatal skin condition score. Based on the distribution we will select the most appropriate link function to fit a generalized linear model with repeated measures. The models to be estimated will be similar to the example model we presented for number of apnea events, including the appropriate link function and distribution. Further, we will remove technology burden scores and add time varying covariates for time since last bath, urine output, stool pattern, and feeding type indicator.

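### The skin event that stops the intervention (NSCS of 5 or more in the diapered area) is not a named outcome, and the planned NSCS slope could miss an excess of it in the 6-hour arm

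*Combined protocol and SAP*

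**What the plan says.** Section 3 gives the reason for the skin work: to understand "any potential skin health trade-offs associated with longer versus shorter time between diapering care".

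Section 8 has the skin watched twice daily. When the NSCS reaches 5 or more because of dryness, erythema or breakdown in the diapered area, "the intervention will be discontinued, the infant's provider will be consulted regarding the need for treatment". The same section then provides for follow-up after the stop: "the infant will be monitored until resolution of the problem".

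Section 4d covers loss of eligibility: "If the infant no longer meets inclusion criteria the intervention will be discontinued and routine data collection will be discontinued". It goes on: "The exclusion criteria will be noted, e.g. use of diaper cream, and data collection regarding any new illness characteristics or treatments will continue". Section 4e, item vii, limits when scores are taken: "The NSCS will be collected twice daily (day and night shift by staff nurses) while infants are participating in the study".

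For the analysis, section 10, Aim 2 RQ2 begins "We will assess the distribution of the neonatal skin condition score", then chooses a link function and fits a repeated-measures generalized linear model like the apnea model. Under Aim 1 RQ2, the estimate of interest in that model is b3, the group-by-day interaction. The opening of section 10 also promises a description of each variable by group. Late onset sepsis and urinary tract infection are compared by log-rank test. Neither Table 1 nor section 10 lists an NSCS of 5 or more, a skin-related stop, diaper cream or diaper rash as an outcome.

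**The concern.** The plan defines an event serious enough to end the intervention and provides for the reason for leaving to be noted, but it names no comparison of that event between arms. The number of infants who reach the threshold is the most direct measure of what a longer diaper interval might cost. A difference in score slopes answers another question. An infant who stops may add one or two high scores and then leave the data, so the arm with more stops need not have the steeper slope. If the slope is the Aim 2 result for skin condition, the report could say no difference was found while clearly more infants in the 6-hour arm had to stop. The stop rate by arm is also something the larger study mentioned in section 4b would need.

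**Working it through.** **The plan's own figures.** Three observations a week for 6 weeks gives 3 × 6 = 18 days, matching section 10. The target of 50 infants (25 per group) cannot be reproduced, because no effect size, standard deviation, event rate or power is stated. All event rates below are therefore assumptions.

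**How many readings a stop supplies.** Twice daily over 42 days is up to 84 scores per infant, so one stopping score is 1/84 = 1.2% of a full record. If 5 of 25 infants stop at day 14 and readings end there, the arm has 20 × 84 + 5 × 28 = 1,820 scores, and the stopping scores are 5/1,820 = 0.27%. This shows how thinly the event is represented. It does not by itself show that a model would miss it, hence the next step.

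**Can the slope show an excess of stops?** Simulation with 25 infants per arm, 300 to 400 runs and two-sided 0.05. The slope b3 was estimated by GEE with exchangeable correlation, robust standard errors, identity link and no covariates, and compared with a log-rank test on time to skin stop. Score distribution, stop rates and timing were assumed.

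| Stop rates; timing | Readings used | b3 significant | Log-rank significant |
|---|---|---|---|
| 10% v 30%; over 6 weeks | end at stop | 9–10% | 45–47% |
| 10% v 30%; first 2 weeks | end at stop | 7% | 42% |
| 10% v 40%; over 6 weeks | end at stop | 12% | 67% |
| 10% v 40%; first 2 weeks | end at stop | 8% | 72% |
| 10% v 30%; over 6 weeks | 3 days of raised scores before stop | 14–15% | 42–46% |
| 10% v 30%; first 2 weeks | 3 days of raised scores before stop | 4% | 38% |
| 10% v 40%; over 6 weeks | 3 days of raised scores before stop | 23% | 70% |
| 10% v 30%; over 6 weeks | 5 days after stop kept | 22–26% | 43–47% |
| 10% v 30%; first 2 weeks | 5 days after stop kept | 10% | 44% |
| 10% v 40%; over 6 weeks | 5 days after stop kept | 48% | 72% |

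With equal stop rates, b3 was significant in 3 to 7% of runs. Simulation error at 10% and 400 runs is √(0.10 × 0.90/400) = 1.5 points. With early stops and readings ending at the stop, the mean b3 was slightly negative. A separate simulation with modest background variation and readings ending at the stop gave 5 to 11% for b3 over both rate pairs, against 27 to 62% for Fisher's exact test on the event.

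A random-intercept mixed model gave 7% at 10% v 30% with spread stops and readings ending at the stop. With 3 days of raised scores before the stop it gave 34%, against 8% with equal rates. With post-stop readings its rejection rate with equal stop rates rose to 24%, so its results there are not relied on.

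**Precision of a direct comparison.** Half-width = 1.96 × √[p₁(1−p₁)/25 + p₂(1−p₂)/25].
- 5% v 20%: 1.96 × √(0.0019 + 0.0064) = 0.18; Fisher power 20%.
- 10% v 30%: 1.96 × √(0.0036 + 0.0084) = 0.21; Fisher power 31%.
- 10% v 40%: 1.96 × √(0.0036 + 0.0096) = 0.23; Fisher power 59%.

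By the usual normal-approximation formula, 80% power would need 76, 62 and 32 infants per arm.

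**The case against.** A reader might infer that skin harm is never compared between arms. The documents do not support that: NSCS, TEWL and pH are all modelled by group, and the general descriptive sentence in section 10 covers NSCS by arm. A proportion at 5 or more could be taken from the charted scores. What stands is that nothing commits the sponsor to report it, and stops and their reasons are not Table 1 variables.

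A reader might also infer that the NSCS model gives these events almost no weight, since one high score hardly moves an infant's mean. That does not follow. If every other score were 3 and each stopped infant had one identical high score at the same point, infant means would be an exact rescaling of the event. With 0/25 v 5/25 stops, a t-test gives t = 2.45, p = 0.018 on either, and Fisher's test gives p = 0.050. A small shift means little until it is set against background variation, which the plan does not give. A comparison of infant means is also not the planned analysis. The case rests on the slope.

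Three further points limit the claim. The link function is left open, so an ordinal or dichotomised model is possible. Monitoring until resolution might feed the model, and the table shows that this raises the slope's chance of detection. Finally, only the NSCS threshold is an explicit skin stop. Section 4d ties stopping to inclusion criteria, diaper rash is listed only as an exclusion criterion (sections 4b and 5), and diaper cream is on neither list. Treating rash or cream as stop events is inference.

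The low power of a direct comparison is conceded. It argues for an interval rather than for leaving the event out, and the plan already accepts event comparisons for sepsis and urinary tract infection at this size.

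**Conclusion.** The point holds in this form. The plan's own skin-harm event is not a named outcome and has no planned between-arm comparison. If readings end at the stop, the group-by-day slope is a poor substitute: at assumed stop rates of 10% v 30% with 25 per arm it was significant in about 5 to 10% of runs, near its null rate. A threefold excess of stops could pass as no difference in Aim 2.

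The size depends on the assumed rates, timing and score distribution, and on a slope analysis without covariates. It shrinks if scores rise for some days before the stop or if later readings are modelled. The absence of a named comparison does not depend on any of these. This is a change that should be made; it does not invalidate the other Aim 2 analyses.

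**What to change.** Add to Table 1 and Aim 2 the outcome *first NSCS of 5 or more in the diapered area leading to discontinuation within 6 weeks of randomisation*, with its date and reason. Report by arm, in all randomised infants, the count and proportion, the risk difference with an exact 95% confidence interval, and the cumulative incidence. State whether infants who leave for other reasons are censored or counted as a competing event. State also whether scores taken after a stop enter the NSCS model.

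List stops noted for other skin reasons, such as diaper cream, separately by arm. Before that, the sponsor must reconcile sections 4b, 4d, 5 and 8 on what stops the intervention; no clinical rule is proposed here.

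The cost is one table row, a few sentences in section 10 and a rule for early leavers. The scores and the reason for stopping are already to be recorded. The downside is a wide interval, about 18 to 23 points either side at 25 per arm, so the result should be presented as an estimate and not as a powered test.

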## 9. Costs to the Subject

There will be no cost to study participants.

### 10. Data Analysis and Statistical Considerations

Initially, we will conduct descriptive analyses, including examination of means and proportions and the measures of variability for each variable overall and by bundled care groups. The descriptive analyses will be followed by modeling approaches to respond to the research questions. Tests of statistical significance will be two-sided and the threshold for statistical significance will be P < 0.05.

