**Exploratory health outcomes** will examine the incidence of late onset sepsis and urinary tract infections in both bundled care groups.

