## Aim 1. Evaluate differences in infant health when diaper changes occur at 3- versus 6-hours?

**RQ1**. What caregiving activities other than diaper changes are included in bundled care events and do they differ when diaper changes are bundled every 3 versus 6 hours **Analysis:** Each day bundled care is observed, a list of activities will be marked as occurred (1) or did not occur (0). Each infant will have 18 days of data denoting whether an activity occurred or did not occur. Hierarchical clustering of repeated data with an appropriate algorithm that

or did not occur. Hierarchical clustering of repeated data with an appropriate algorithm that producing stable and accurate clusters will be used will be to determine the groupings of activities that occur in the sample. The frequency of the clusters between the intervention groups will be compared.

**RQ2**. Does infant physiological stability ( $\Delta$  heart rate,  $\Delta$  respiratory rate,  $\Delta$  oxygen saturation, # apnea # bradycardias, # desaturations, feeding tolerance) differ between 3- and 6-hour bundled care diapering?

**Analysis:** Heart rate, respiratory rate and oxygen saturation values captured a minute apart for each observed bundled care with a diaper change will be graphically displayed in various constructions to be able to compare the general trends of change in these outcomes between intervention groups, among periods of the bundled care (before, during and after) and over weeks. Further, we will create a daily average of each outcome by period (before, during, and after). Using a repeated measures analysis, we will test for difference among the periods and intervention group and all pairwise period comparisons between groups. PMA and infant illness severity (Technology Burden Score) will be used as a covariate. We will control for multiple comparisons.

A Poisson Generalized linear model for repeated measure will be use to estimate the daily number of apnea, bradycardias, and desaturations events over the 18 days of bundled care observations with a diaper change. The need for a random intercept or slope will be assessed.

 $Log(\# of Apnea Events_{ij}) = b_0 + b_1[I(6HrBC_i)] + b_2(Day_{ij}) + b_3[(I(6HrBC_i)) \times (Day_{ij}) + b_4(PMA_{ij}) + b_5(TechBur_{ij}),$ 

where  $Log((\# of Apnea Events_{ij}))$  is the logarithm of the number of apnea events for individual i at day j.  $b_0$  is the mean log of apnea events for participants who receive 3-hour diaper changes

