and are mean postmenstrual age and with mean technology scores at the start of the study;  $b_1$  is the change in log number of apnea events for those receiving 6-hour diaper changes;  $I(6HrBC_i)$  is an indicator for participants receiving bundled care and 6-hour diaper changes;  $b_2$  is the change in log of the number of apnea events for each day of bundled care;  $Day_{ij}$  is the indicator of the day the number of apnea events was recorded;  $b_3$  is the additional change in log of the number of apnea events over days for those receiving bundled care and 6-hour diaper changes;  $PMA_{ij}$  is the difference from the baseline mean postmenstrual age of the ith participant at the jth day;  $TechBur_{ij}$  is the difference from the baseline mean technology burden score for the ith participant at the jth day;  $b_4$  and  $b_5$  are the expected changes in log number of events for postmenstrual age and technology burden scores, respectively. The estimate of interest is  $b_3$ . The feeding tolerance outcome will be estimated in a similar manner using the appropriate distribution of the outcome and link function for the model.

**RQ3**. Does infant weight gain over time differ between 3- and 6-hour bundled care diapering? **Analysis:** The trajectories of weight measured across the 18 days of bundle care will be fitted using a linear mixed model with a random intercept. We will first determine the best trajectory fit for weight over the 18 days. Once we select an appropriate trend for the data a model similar to the one described below will be estimated.

$$Weight_{ij} = b_0 + b_{i0} + b_1[I(6HrBC_i)] + b_2(Day_{ij}) + b_3[(I(6HrBC_i)) \times (Day_{ij}) + b_4(PMA_{ij}) + b_5(TechBur_{ij}) + \\ \epsilon_{ii},$$

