## **RQ3**. Does skin pH differ over time and at the end of 6 weeks between 3- and 6-hour bundled care diapering on the buttocks and chest?

**Analysis:** We will assess the distribution of the pH of chest and buttocks. Based on the distribution, we will select the most appropriate link function to fit a generalized linear model with repeated measures. The models to be estimated will be similar to the example model we presented for number of apnea events, including the appropriate link function and distribution. Further, we will remove technology burden scores and add time varying covariates for time since last bath, urine output, stool pattern, and feeding type indicator. Separate models will be estimated for pH of the chest and pH of the buttocks.

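### One P < 0.05 threshold covers nine or ten unranked, unadjusted between-arm tests in a study whose stated purpose is exploration and estimation

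*Combined protocol and SAP*

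**What the plan says.** The opening paragraph of Section 10 applies one standard to all the modelling that follows: "Tests of statistical significance will be two-sided and the threshold for statistical significance will be P < 0.05".

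The analysis paragraphs then list the outcomes without ranking them.

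- **Aim 1 RQ2, vital signs.** Heart rate, respiratory rate and oxygen saturation are compared by period and group, with the promise "We will control for multiple comparisons". The same sentence recurs in RQ4, which is a comparison within the 6-hour arm. Neither place names a method or a family of tests.
- **Aim 1 RQ2, events and feeding.** "A Poisson Generalized linear model for repeated measure will be use to estimate the daily number of apnea, bradycardias, and desaturations events". Then: "The feeding tolerance outcome will be estimated in a similar manner". No adjustment is stated.
- **Aim 1 RQ3.** A mixed model for weight, with no adjustment stated.
- **Aim 2 RQ1 to RQ3.** Models for TEWL, NSCS and pH, with no adjustment stated. For pH, "Separate models will be estimated for pH of the chest and pH of the buttocks". For TEWL, the question names both sites but the analysis describes a single model.

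Within the apnea and weight models, the group-by-day coefficient b3 is named as the estimate of interest, and the other models are to be built along similar lines. The exploratory label in Section 2 is attached only to the outcomes that "will examine the incidence of late onset sepsis and urinary tract infections in both bundled care groups".

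**The concern.** The background section expects outcomes that may pull in opposite directions: less stress from fewer diaper changes, set against "any potential skin health trade-offs associated with longer versus shorter time between diapering care". With nine or ten outcomes of equal standing, each judged at 0.05, one nominally significant result could be reported as a difference for or against 6-hour diapering. Nothing in the plan says how much weight that result should carry. The study is meant to inform a larger trial, so a chance finding could steer that trial's choice of outcome or its assumed effect.

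**Working it through.** **Inputs from the documents.** Two-sided 0.05 per test (Section 10). Between-arm model tests without stated adjustment (Section 10, Aims 1 and 2):

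| Outcome | Tests |
|---|---|
| Apnea, bradycardia, desaturation | 3 |
| Feeding tolerance | 1 |
| Weight | 1 |
| TEWL | 1 if both sites share a model, 2 if separate |
| NSCS | 1 |
| pH, chest and buttocks | 2 |
| **Total k** | **9 or 10** |

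The count leaves out the microbiota comparisons, the activity clusters, and the two infection outcomes labelled exploratory.

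**Assumption.** The documents give no correlation between the test statistics, so I show a range from 0 to 0.9. The plan states no family-wise error rate to reproduce. With k = 1 the formula returns the stated 5%.

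**Independent tests.** The chance of at least one false positive when no true difference exists is 1 − 0.95^k:

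- k = 9: 1 − 0.95^9 = 0.370
- k = 10: 1 − 0.95^10 = 0.401

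The expected number of false positives is 9 × 0.05 = 0.45 or 10 × 0.05 = 0.50, whatever the correlation.

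**Equally correlated tests.** For normal test statistics with common correlation r and c = 1.96, the chance is

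1 − ∫ φ(z) [Φ((c − √r z)/√(1 − r)) − Φ((−c − √r z)/√(1 − r))]^k dz.

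| k | r = 0 | r = 0.5 | r = 0.9 |
|---|---|---|---|
| 9 | 37.0% | 26.9% | 12.4% |
| 10 | 40.1% | 28.7% | 12.8% |

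The lowest entry, 12.4%, is 2.47 times 5%.

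**Correlation only among related outcomes.** Take k = 10, with correlation only within the three event counts, between the two TEWL sites and between the two pH sites. Simulation gives 39% when that correlation is 0.3 and 32% when it is 0.9. This structure is more plausible than one common correlation of 0.9 across weight, apnea and skin pH.

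**The case against.** The strongest reply is that this is an exploratory study by its own account. Sections 2 and 3 describe the purpose as exploring impact. Section 4b gives the goal as estimating values and variances for a larger study, and Section 8 says benefits will become clear only in larger studies. Many statisticians would not require family-wise control across separate research questions in such a study. That stands, and it limits the harm to a mislabelled difference. It does not explain why Section 10 sets a formal significance threshold without saying that results below it are hypothesis-generating, or why only sepsis and urinary tract infection are called exploratory.

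Three stronger readings are tempting, but the documents do not support them.

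- **That no contrast is specified at all.** b3 is the named estimate in the apnea and weight models, and the other models follow them. What is missing is a ranking across outcomes.
- **That ten tests is the minimum, or that there are 17.** Separate site models are stated only for pH, so TEWL may be one test and the floor is nine. Seventeen would need three separate feeding-tolerance models and a separate week-6 test for each of five skin outcomes. The week-6 question is posed, but the analysis paragraphs specify no such test, and feeding tolerance is described as one outcome.
- **That the trial is a confirmatory study that fails to control its error rate.** Nothing in the documents presents it as confirmatory.

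**Conclusion.** The concern holds as a conflict between the stated purpose and the stated decision rule. Followed as written, the rule gives a chance of at least one false arm difference of about 37–40% under independence, 27–29% at correlation 0.5 and 12–13% at 0.9. These figures assume no true effect on any of the nine or ten outcomes, tests that each hold their nominal 5% level, and a correlation that the documents do not supply. The exact count and correlation change the size but not the conclusion. The defect affects what may be claimed from the results; it does not affect the value of the estimates.

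**What to change.** Amend the opening of Section 10 so that the Aim 1 and Aim 2 between-arm comparisons are reported as estimates with 95% confidence intervals and labelled hypothesis-generating, with no significance claim resting on an individual P < 0.05. This matches the estimation goal in Section 4b.

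If the sponsor wants a significance claim, it should name one lead outcome before any data by arm are seen, use the b3 group-by-day contrast already specified, and apply the 0.05 threshold to that contrast alone. If it wants one lead outcome per quantitative aim, it should test the two with Holm at an overall 0.05.

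A week-6 value should not be the default lead contrast. The inclusion criteria ask for an expected stay of only 4 weeks (Section 4b) or 2 weeks (Section 5), and Section 4d stops routine data collection when an infant no longer meets the criteria. Week 6 is therefore the point most exposed to missing data.

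Keep the vital-sign adjustment for its pairwise period comparisons.

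**Cost.** Wording only: no extra infants or data. Nominal P < 0.05 results on the other outcomes could no longer be reported as significant. With Holm over two contrasts, the smaller P value must be below 0.025. In a simple two-group approximation with 25 per arm and 80% power, the detectable difference at that first step rises from (1.960 + 0.842) × √(2/25) = 0.79 SD to (2.241 + 0.842) × √(2/25) = 0.87 SD. A single lead contrast stays at 0.79 SD.
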